6.4.3.3 Ribociclib/everolimus dose modification and management for cardiac dysfunction

Table 6-10 Ribociclib/everolimus dose modification and management for cardiac dysfunction

(see [Table 6-5](#) and [Table 6-6](#) for dose reduction guide)

Adverse drug reaction	Severity	Dose adjustment and management recommendations
Cardiac - Left Ventricular Systolic Dysfunction	Asymptomatic, resting ejection fraction 40-50%; or 10-20% drop from baseline	Maintain dose level, and continue ribociclib and everolimus with caution. Repeat LVEF within 4 weeks or as clinically appropriate.
	Symptomatic, responsive to intervention, ejection fraction 20-39% or >20% drop from baseline	Hold ribociclib and everolimus until resolved, then reduce study treatment by one dose level; LVEF measurement to be repeated, if not resolved within 28 days permanently discontinue ribociclib and everolimus if applicable.

6.4.3.4 Ribociclib/everolimus dose modification and management for hepatotoxicity's

Table 6-11 Ribociclib/everolimus dose modification and management for hepatotoxicity

(see [Table 6-5](#) and [Table 6-6](#) for dose reduction guide)

HEPATOTOXICITY (BILIRUBIN, SGPT/ALT, SGOT/AST)	
TOTAL BILIRUBIN without ALT/AST increase above baseline value	
Grade 1 (> ULN – 1.5 x ULN) (confirmed 48 to 72hrs later)	If confirmed, maintain dose level with LFTs monitored bi-weekly until normalizes.
Grade 2 (>1.5 – 3.0 x ULN)	Dose interruption of ribociclib and everolimus If resolved to ≤grade 1 in ≤21 days, then maintain dose level If resolved to ≤grade 1 in >21 days or toxicity recurs, lower 1 dose level,.Repeat liver enzymes and bilirubin tests twice weekly for 2 weeks after dose resumption If toxicity recurs after two dose reductions, discontinue study treatment

Grade 3 (>3.0 – 10.0 x ULN)	Dose interruption of ribociclib and everolimus If resolved to ≤ Grade 1 in ≤21 days, lower 1 dose level. Repeat liver enzymes and bilirubin tests twice weekly for 2 weeks after dose resumption If resolved to ≤grade 1 in >21 days or toxicity recurs, discontinue study treatment
Grade 4 (>10.0 x ULN)	Discontinue ribociclib Confounding factors and/or alternative causes for increase of total bilirubin should be excluded before dose interruption/reduction. They include but are not limited to: evidence of obstruction, such as elevated ALP and GGT typical of gall bladder or bile duct disease, hyperbilirubinemia due to the indirect component only (i.e. direct bilirubin component ≤1 x ULN) due to hemolysis or Gilbert's Syndrome, pharmacologic treatment, viral hepatitis, alcoholic or autoimmune hepatitis, other hepatotoxic drugs. For patients with Gilbert's Syndrome, these dose modifications apply to changes in direct bilirubin only. Bilirubin will be fractionated if elevated.

HEPATOTOXICITY (AST or ALT)	
AST or ALT without bilirubin elevation >2 x ULN	
Same grade as baseline or increase from baseline grade 0 to grade 1	No dose adjustment required with LFTs monitored per protocol if same grade as baseline or bi-weekly in case of increase from baseline grade 0 to 1

6.4.3.4.1 Additional follow-up for hepatic toxicities

Hepatic toxicity monitoring includes assessment of the following liver function tests (LFTs): albumin, ALT, AST, total bilirubin, direct and indirect bilirubin alkaline phosphatase (fractionated if alkaline phosphatase is grade 2 or higher), creatinine kinase, prothrombin time (PT)/(PTT), international normalized ratio (INR) and Gamma-glutamyl transpeptidase (GGT). For patients with Gilbert's Syndrome: total and direct bilirubin must be monitored, intensified monitoring applies to changes in direct bilirubin only. Close observation is recommended in case of AST, ALT, and/or bilirubin increase requiring dose interruption, which involves: Repeating liver enzyme and serum bilirubin tests **approx. two times weekly**. Frequency of re-testing can decrease to once a week or less if abnormalities stabilize or return to normal values.

- Obtaining a more detailed history of current symptoms.
- Obtaining a more detailed history of prior and/or concurrent diseases including history of any pre-existing liver conditions or risk factors.
- Obtaining a history of concomitant drug use (including non-prescription medications, herbal and dietary supplements), alcohol use, recreational drug use, and special diets.
- Ruling out acute viral hepatitis types A, B, C, D, and E; hepatotropic virus infections cytomegalovirus (CMV), Epstein-Barr virus (EBV), or herpes simplex virus (HSV); autoimmune or alcoholic hepatitis; NASH; hypoxic/ischemic hepatopathy; and biliary tract disease.
- Obtaining a history of exposure to environmental chemical agents.
- Obtaining additional tests to evaluate liver function, as appropriate (e.g., INR, direct bilirubin).
- Considering gastroenterology or hepatology consultations.

- Assessing cardiovascular dysfunction or impaired liver oxygenation, including hypotension or right heart failure as possible etiologies for liver dysfunction.
- Obtaining a PK sample, as close as possible to last dose of study drug.
- Liver biopsy as clinically indicated to assess pathological change and degree of potential liver injury.

Increase in transaminases combined with total bilirubin (TBIL) increase may be indicative of drug-induced liver injury (DILI), and should be considered as clinically important events. The threshold for potential DILI may depend on the patient's baseline AST/ALT and TBIL value; patients meeting any of the following criteria will require further follow-up as outlined below:

- For patients with normal ALT AND AST AND TBIL value at baseline: AST or ALT $>3.0 \times \text{ULN}$ combined with TBIL $>2.0 \times \text{ULN}$.
- For patients with elevated AST or ALT or TBIL value at baseline: [AST or ALT $>2 \times \text{baseline AND } >3.0 \times \text{ULN}$] OR [AST or ALT $>8.0 \times \text{ULN}$], whichever is lower, combined with [TBIL $>2 \times \text{baseline AND } >2.0 \times \text{ULN}$].

Medical review needs to ensure that liver test elevations are not caused by cholestasis, defined as: Alkaline phosphatase (ALP) elevation $>2.0 \times \text{ULN}$ with R value <2 in patients without bone metastasis, or elevation of ALP liver fraction in patients with bone metastasis.

Note: The R value is calculated by dividing the ALT by the ALP, using multiples of the ULN for both values [R value = ALT/ULN)/(ALP/ULN)]. It denotes the relative pattern of ALT and/or ALP elevation is due to cholesteric or hepatocellular liver injury or mixed type injury.

In the absence of cholestasis, these patients should be immediately discontinued from study drug treatment, and repeat LFT testing as soon as possible, preferably within 48 hours from the awareness of the abnormal results. The evaluation should include laboratory tests, detailed history, physical assessment and the possibility of liver metastasis or new liver lesions, obstructions/compressions, etc.

All cases confirmed on repeat testing meeting the laboratory criteria defined above, with no other alternative cause for LFT abnormalities identified, should be considered as "medically significant", thus met the definition of SAE ([Section 8.2](#)), and reported as SAE using the term "potential drug-induced liver injury". All events should be followed up with the outcome clearly documented.

6.4.4 Dose modification and management for everolimus specific toxicities

Table 6-12 Everolimus specific toxicities management and recommendations

(Refer to dose modification [Table 6-5](#) and [Table 6-6](#))

Adverse drug reaction	Severity	Dose adjustment and management recommendations
Stomatitis	Grade 1	No dose adjustment required.

Adverse drug reaction	Severity	Dose adjustment and management recommendations
	Minimal symptoms, normal diet	Manage with non-alcoholic steroid mouthwash and salt water (0.9%) mouth wash four times a day.
	Grade 2 Symptomatic but can eat and swallow modified diet	Interrupt everolimus and ribociclib until recovery to grade 1. Re-initiate study treatment at the same dose. If stomatitis recurs, interrupt ribociclib and everolimus until recovery to grade 1. Re-initiate study treatment at a one dose lower. Manage with topical analgesic mouth treatments (e.g. benzocaine, butyl minobenzoate, tetracaine hydrochloride, menthol or phenol) with or without topical corticosteroids (i.e. triamcinolone oral paste).
	Grade 3 Symptomatic and unable to adequately aliment or hydrate orally	Interrupt everolimus and ribociclib until recovery to grade ≤1. Re-initiate study treatment at a reduced dose; If reoccurs, interrupt ribociclib and everolimus until recovery to grade ≤1. Re-initiate study treatment at second dose level. Manage with topical analgesic mouth treatments (i.e. benzocaine, butyl aminobenzoate, tetracaine hydrochloride, menthol or phenol) with or without topical corticosteroids (i.e. triamcinolone oral paste).
	Grade 4 Symptoms associated with life-threatening consequences	Hold ribociclib and everolimus and provide appropriate medical therapy. If recovered to ≤grade 1 within 3 weeks, Re-initiate study treatment at a reduced dose. If >3 weeks, then discontinue study treatment.
Serum creatinine	Grade 1	No dose adjustment required. Initiate appropriate monitoring.

Adverse drug reaction	Severity	Dose adjustment and management recommendations
	Grade 2	Hold ribociclib and everolimus until resolved to grade ≤1, then re-initiate study treatment at the same dose level. If toxicity recurs at Grade 2, interrupt ribociclib and everolimus until recovery to grade ≤1, re-initiate and study treatment by one dose level.
	Grade 3	Hold ribociclib and everolimus until resolved to grade ≤1, then reduce study treatment by 1 dose level. If toxicity recurs after two dose reductions, discontinue study treatment
	Grade 4	Discontinue study treatment and manage appropriately.
Metabolic events (e.g. hyperglycemia, dyslipidemia)	Grade 1	No dose adjustment required. Initiate appropriate medical therapy and closely monitor. Consider metformin for hyperglycemia
	Grade 2	No dose adjustment required. Manage with appropriate medical therapy and monitor. For hyperglycemia, consider metformin and follow up with endocrinologist
	Grade 3	Hold ribociclib and everolimus until resolved to grade ≤1, then reduce study treatment by 1 dose level; Manage with appropriate medical therapy and monitor.
	Grade 4	Hold ribociclib and everolimus until resolved to grade ≤1 then discontinue study treatment

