6.3.1.2 Dexamethasone treatment regimen

Cycle 1 Day 1 (C1D1) is the day the patient initiates the mouthwash regimen and study drugs. A treatment cycle consists of 28 days. Patients should use mouthwash regimen for two consecutive treatment cycles (56 days).

All patients will be instructed to perform routine “good oral care” each day during the trial. Good oral care will consist of: brushing teeth at least twice daily with soft bristled toothbrush continue current daily flossing routine (if patients were not already flossing daily, they should not be instructed to start flossing as this could cause oral trauma), and continue routine dental care/maintenance with their dentist, if they have one.

Salt water mouth rinse and the steroid mouthwash should be administered based on the following instructions:

- The Salt water mouth rinse will only be administered once the onset of Grade 1 stomatitis has been noted.

If the salt water (0.9%) mouth rinse is needed, it will be administered as 10mL swish and spit TID and must be done prior to the dexamethasone mouthwash. The patient should administer the salt water (0.9%) mouth rinse (swish and spit) and wait for 10-15 minutes before administering the dexamethasone mouthwash.

The alcohol-free, 0.5mg/5mL dexamethasone steroid mouthwash should be administered based on the following instructions:

- 10 mL of mouthwash swish and spit TID. The mouthwash is to be held in mouth and swished around mouth to come in contact with entire buccal mucosa surface for a minimum of two minutes, and then spit out.
- Patient should remain NPO (no food, no drinks, nothing in mouth) for at least an hour after administering mouthwash, with the exception of Nystatin (or another topical antifungal).

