6.4.6 Guidance for all other adverse reactions

Consider performing an analysis of serum potassium, calcium, phosphorus, and magnesium for all adverse reactions, if indicated. If electrolyte values are outside of the normal range, interrupt ribociclib/everolimus administration, correct electrolytes with supplements or appropriate therapy as soon as possible, and repeat electrolyte testing until documented normalization of the electrolytes.

Table 6-16 Ribociclib/everolimus dose adjustment and management recommendation for all other adverse reactions

(see [Table 6-5](#) and [Table 6-6](#) for dose reduction guide)

Grade/Severity	Dose adjustment and management recommendations
Grade 1	No dose adjustment- maximize AE management
Grade 2	Dose interruption of ribociclib/everolimus until recovery to Grade ≤1 Initiate appropriate medical therapy and monitor Re-initiate study treatment at the same dose If the same toxicity recurs at Grade 2, interrupt ribociclib/everolimus until recovery to Grade ≤1. Re-initiate study treatment at the next lower dose level.
Grade 3	Hold both everolimus and ribociclib until it resolves to ≤Grade 1. Initiate appropriate medical management and monitor Re-initiate study treatment at the next lower dose level If toxicity recurs at grade 3, discontinue study treatment
Grade 4	Discontinue study treatment
Additional recommendations (see supplementary management brochure for further recommendations):	
Nausea: Ensure adequate hydration or fluid repletion. Consider performing an analysis of serum potassium, calcium, phosphorus and magnesium, if indicated. If electrolyte values are below LLN, interrupt ribociclib, correct electrolytes with supplements as soon as possible, and repeat electrolyte testing until documented normalization.	

Diarrhea: At the first sign of loose stools (Grade 1), initiate loperamide. Patient should remain well hydrated. Fluids and electrolytes should be replaced as needed. Consider performing an analysis of serum potassium, calcium, phosphorus and magnesium, if indicated. If electrolyte values are below LLN, interrupt ribociclib, correct electrolytes with supplements as soon as possible, and repeat electrolyte testing until documented normalization.

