6.5.3 Permitted concomitant therapy requiring caution and/or action while on study

Permitted medications to be used with caution combined ribociclib + everolimus + exemestane treatment in this study ([Appendix 1, Table 14-2](#)) are listed below. These medications should be excluded from patient use if possible. If they must be given based on the investigator's judgment, then use with caution and consider a ribociclib interruption if the concomitant medication is only needed for a short time:

- Moderate inhibitors or inducers of CYP3A4/5.
- Sensitive substrates of CYP3A4/5 that do not have narrow therapeutic index.
- Strong inhibitors of BSEP.
- Medications that carry a possible risk for QT prolongation.
- Sensitive substrates of the renal transporters, MATE1 and OCT2.
- Sensitive substrates of BCRP (has a potential to increase exposure to substrates of these transporters, although no animal or clinical data are available to support these statements)

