Sensitive CYP3A4/5 substrates ¹	Alpha-dihydroergocryptine, apixaban, aprepitant, atorvastatin, avanafil, bosutinib, brotizolam, budesonide, buspirone, cobimetinib, darifenacin, dasatinib, ebastine, eletriptan, eplerenone, everolimus, felodipine, fluticasone, grazoprevir, ibrutinib, isavuconazole, ivabradine, ivacaftor, lumefantrine, lurasidone, maraviroc, midazolam, midostaurin, naloxegol, neratinib, perospirone, quetiapine, ridaforolimus, rivaroxaban, sildenafil, simeprevir, ticagrelor, tilidine, tolvaptan, triazolam, ulipristal, vardenafil, venetoclax, vicriviroc, voclosporin-
BSEP inhibitors	Alectinib, atorvastatin, bromocriptine, candesartan, clobetasol, clofazimine, dabigatran, dipyridamole, glyburide, grazoprevir, ledipasvir, mifepristone, pioglitazone, reserpine, rifamycin, simeprevir, telmisartan, timcodar, troglitazone, valinomycin, velpatasvir

Category	Drug Name
Medications that carry a possible risk for QT prolongation ²	Alfuzosin, apomorphine, aripiprazole, artenimol+piperaquine, asenapine, atazanavir, atomoxetine, bedaquiline, bendamustine, bortezomib, bosutinib, buprenorphine, cabozantinib, capecitabine, ceritinib, clomipramine, crizotinib, clozapine, cyamemazine (cyamepromazine), dabrafenib, dasatinib, degarilix, delamanid, desipramine, dexmedetomidine, dolasetron, efavirenz, eliglustat, epiubicin, eribulin mesylate, ezogabine(retigabine), famotidine, felbamate, fingolimod, flupentixol, gemifloxacin, granisetron, hydrocodone-ER, iloperidone, imipramine (mepipramine), isradipine, ketanserin, lapatinib, lenvatinib, leuprolide, loperamide, lithium, melperone, midostaurin, mifepristone, mirabegron, mirtazapine, moexipril/HCTZ, necitumumab, nilotinib, norfloxacin, nortriptyline, nusinersen, ofloxacin, lanzapineosimertinib, oxytocin, paliperidone, palonosetron, panabinstat, pasireotide, pazopanib, perflutren lipid microspheres, perphenazine, pilsicainide, pimavanserin, pipamperone, promethazine, prothipendyl, quetiapine, ranolazine rilpivirine, risperidone, romidepsin, sertindole, sorafenib, sunitinib, tamoxifen, telavancin, tetrabenazine, tipiracil/trifluridine, tizanidine, tolterodine, oremifene, trimipramine, tropisetron, vardenafil, vemurafenib, venlafaxine, vorinostat, ziprasidone
MATE1/2 substrates ³	Acyclovir, cephalexin, cimetidine, fexofenadine, ganciclovir, glycopyrronium, metformin, pindolol, plisicainide, ranitidine, topotecan, varenicline

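### Two toxicity-care instructions are each given in conflicting forms: which drugs to hold for abnormal electrolytes with nausea or diarrhea, and how often to use the salt-water rinse at Grade 1 stomatitis

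*Protocol*

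**What the plan says.** **Electrolytes.** Protocol Section 6.4.6 opens with guidance meant for every adverse reaction: "If electrolyte values are outside of the normal range, interrupt ribociclib/everolimus administration". Under Table 6-16, in the same section, the notes on nausea and on diarrhea each say: "If electrolyte values are below LLN, interrupt ribociclib, correct electrolytes with supplements as soon as possible". The grade rows of Table 6-16 leave the dose alone at Grade 1, interrupt both ribociclib and everolimus at Grades 2 and 3, and end study treatment at Grade 4. Table 6-9, which covers QTcF prolongation, holds both drugs when an electrolyte is outside the normal range, whatever the QTcF grade.

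**Mouth rinse.** Section 6.3.1.2 sets the trigger: "The Salt water mouth rinse will only be administered once the onset of Grade 1 stomatitis has been noted". It then sets the frequency: "If the salt water (0.9%) mouth rinse is needed, it will be administered as 10mL swish and spit TID". The Grade 1 stomatitis row of Table 6-12 says: "Manage with non-alcoholic steroid mouthwash and salt water (0.9%) mouth wash four times a day". That row asks for no change in study-drug dose. The dexamethasone mouthwash itself is three times a day for two cycles (56 days) in Table 6-1 and Sections 6.3.1.1 and 6.3.1.2.

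**The concern.** In both places the protocol gives two rules for one event and does not say which governs. Section 12 allows no authorized deviations, so a site that follows one page departs from the other. The synopsis plans for about 30 sites, and each will settle the matter for itself.

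The electrolyte conflict carries more weight. The protocol makes electrolyte correction part of QTcF management (Table 6-9) and excludes patients with uncorrected low potassium or magnesium (Section 5.3, criterion 24). Dose interruptions and dose intensity are listed among the secondary endpoints of both phases (Tables 3-1 and 3-2), and the SAP reports them drug by drug (Sections 3.2.1, 3.2.3 and 3.8.4.5). If some sites hold everolimus for an abnormal electrolyte and others do not, those summaries partly reflect which paragraph was read.

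**Working it through.** The plan states no figure to reproduce here. The check sets the passages side by side and asks in which patients they lead to different actions.

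**(a) Electrolytes**

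| Situation | Section 6.4.6 text | Notes under Table 6-16 | Same action? |
|---|---|---|---|
| Grade 1 nausea or diarrhea, value below LLN | ribociclib and everolimus | ribociclib only | No: 2 drugs versus 1 |
| Grade 1 nausea or diarrhea, value above range | ribociclib and everolimus | silent | No: interruption versus no instruction |
| Grade 2 or 3 nausea or diarrhea | both drugs | both, through the grade rows | Yes, while the event lasts |
| Grade 4 | study treatment already ended | study treatment already ended | Yes |
| QTcF prolongation | both, and Table 6-9 agrees | – | Yes, by Table 6-9 |

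The two rules differ in the drugs held and in the trigger, and the difference falls mainly on Grade 1 events. It is mainly rather than only, because the hold in the Grade 2 and 3 rows ends when the event recovers to Grade 1 or better. The electrolyte rules run until the values are normal, so the conflict can reopen if a value is still abnormal at that point.

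The route to the data is direct. SAP Section 3.2.1 divides the cumulative dose of each drug by the days on which it should have been taken, counting no-dose days. At a constant planned dose over one 28-day cycle, d held days give a relative dose intensity of (28 − d)/28. Each held day therefore costs 1/28 = 3.6 percentage points of that cycle's everolimus intensity under one rule and nothing under the other. The documents do not say how many patients or days are involved, so no total can be given.

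**(b) Salt-water rinse**

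- Same trigger: onset of Grade 1 stomatitis (Section 6.3.1.2) and the Grade 1 row (Table 6-12).
- Frequency: 3 a day versus 4 a day. This is a direct conflict.
- Steroid mouthwash: if the four-times-a-day phrase in Table 6-12 covers both products, it also conflicts with the three-times-a-day steroid schedule, but only in the first 56 days. If it covers the salt water alone, the steroid schedule stands. Section 6.3.1.2 places each salt-water rinse before a steroid rinse, so one of four salt-water rinses would then have no partner.

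How often the stomatitis row is met can only be given as a range, and none of these figures is specific to Grade 1:

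- 67% with everolimus + exemestane (Section 2.1.2.1)
- 42/77 = 55% in the earlier triplet study (Table 1-6)
- mucositis in 2/16 = 12.5% in cohorts A and B of this trial (Table 1-7)

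**The case against.** The best defence is that both conflicts are narrow. Table 6-16 stops both drugs at Grades 2 and 3 anyway, electrolyte testing is only to be considered where indicated, and Table 6-9 takes over once QTcF is prolonged. The rinse row changes no study-drug dose. All of this stands and sets the size of the point. It does not remove the conflict: nothing marks the nausea and diarrhea notes as exceptions to the general text, and they do not address high values.

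Three stronger readings are tempting, and the documents do not support them.

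- **Metformin.** Table 6-12 says "Consider metformin for hyperglycemia", while Section 6.5.3 says of its drug classes "These medications should be excluded from patient use if possible", and Table 14-2 lists metformin ("ganciclovir, glycopyrronium, metformin, pindolol", and again under OCT2). A reader might call this a third contradiction. It is not. Section 6.5.3 is headed as permitted therapy and leaves use to the investigator, metformin is absent from the prohibited list in Table 14-1, and a site can follow both passages. What is missing is a cross-reference.
- **Adverse-event grade.** A reader might infer that three versus four rinses changes stomatitis grade, and through it holds or dose intensity. Nothing in the documents shows this.
- **Frequency.** Taking 67% as the share of patients affected would borrow a figure from a doublet. All patients here receive the steroid mouthwash, and the trial's own early count is 2 of 16.

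**Conclusion.** The point holds for two drafting contradictions. The electrolyte one matters more: one drug versus two, and low values versus any value outside range, chiefly in Grade 1 nausea or diarrhea. It can make everolimus interruptions and intensity differ by site; by how much is unknown. The rinse one, 3 versus 4 a day, is confined to supportive care, and its extension to the steroid mouthwash depends on the reading and on the first 56 days. Neither bears on the clinical benefit rate, its test or the sample size.

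The conclusion assumes that the slash in ribociclib/everolimus means both drugs, as Table 6-9 spells out. If it were read as either drug, the difference in trigger would remain. No view is taken on which hold rule or which frequency is right.

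**What to change.** Reconcile the opening text of Section 6.4.6 with the nausea and diarrhea notes under Table 6-16, and with Table 6-9, on which drugs are held and at which values. Reconcile Table 6-12 with Section 6.3.1.2 on salt-water frequency, and state whether the frequency in Table 6-12 also applies to the steroid mouthwash. There should be one instruction per event, chosen by the clinical team. A pointer from the metformin entries in Table 6-12 to Section 6.5.3 and Table 14-2 is optional.

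The cost is a wording change. Section 12.1 requires a written amendment for any protocol change, so it can go with the next one, and a letter can alert sites meanwhile. No analysis or sample-size change follows. Amendment 3 records 104 patients already enrolled, so the correction helps only those still on treatment. For the others, the report should note that everolimus interruptions linked to electrolytes were recorded under two differing instructions.
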